ClinicalTrials.gov PRS DRAFT Receipt (Working Version)

Last Update: 05/25/2022 18:02

ClinicalTrials.gov ID: [Not yet assigned]

Study Identification

Unique Protocol ID: TUN IRB4-10-13A

Brief Title: Physiological Responses to Osteopathic Manipulative Techniques in Healthy Young Adults

Official Title: Physiological Responses to Osteopathic Manipulative Techniques in Healthy Young Adults

Secondary IDs:

Study Status

Record Verification: April 2022

Overall Status: Completed

Study Start: October 4, 2013 [Actual]

Primary Completion: August 7, 2019 [Actual]

Study Completion: August 7, 2019 [Actual]

Sponsor/Collaborators

Sponsor: Touro University Nevada

Responsible Party: Principal Investigator

Investigator: [name] [[name]]

Official Title: Assistant Professor

Affiliation: Touro University Nevada

Collaborators:

Oversight

U.S. FDA-regulated Drug: No

U.S. FDA-regulated Device: No

U.S. FDA IND/IDE: No

Human Subjects Review: Board Status: Approved

Approval Number: IRB4-10-13A, IRB 8-09-17A

Board Name: Touro University Nevada IRB

Board Affiliation: Touro University Nevada

[contact]

Email: [contact]

Address:

Touro University Nevada
[name]
[name]

Data Monitoring: No
FDA Regulated Intervention: No

Study Description

Brief Summary: This study was designed to investigate the effect of selected osteopathic manipulative techniques (OMT) on cardiovascular functions in healthy young men and women.

This work addressed questions regarding physiological responses to OMT in maintaining the cardiovascular homeostasis by (1) measuring changes in the cardiac autonomic nerves activity, (2) measuring changes in cardiovascular parameters such as blood pressure, cardiac contractility, and heart rate, and (3) investigating if changes in the cardiac autonomic nerves activity were related to changes in blood pressure, cardiac contractility, or heart rate.

This controlled not-randomized pilot study with repeated measures was conducted at the Touro University Nevada College of Osteopathic Medicine. Healthy 21-35 years old students and employees volunteered in the study. The experimental group received the three cranial osteopathic manipulative techniques, namely, occipital-atlantal decompression, occipital-mastoid decompression, and compression of the fourth ventricle, consecutively applied. This study included two control groups; one group received sham manipulations, and the second group did not receive any manipulations and was the non-touch group.

The computerized MP150 BIOPAC System was used for data collection and analysis. The skin electrodes were used for the one-lead ECG and impedance cardiography. Digital data were recorded during the entire experimental protocol. The blood pressure was measured manually before and after the experimental procedure using blood pressure cuff and stethoscope. Cardiovascular responses to OMT were evaluated by using the heart rate variability test (HRV), calculating changes in cardiac contractility, and comparing changes in pre- and post- blood pressure readings.

An analysis of variance (ANOVA) with a Bonferroni post-hoc test was used to evaluate treatment effects. The type I error rate (alpha) was set at 0.05.

Detailed Description: Healthy, 21-35 years old, male and female volunteers were recruited from Touro University students, faculty and staff using a brochure, poster, e-mail and personal conversation. Each participant signed an informed consent form. Participants were allowed to participate in multiple experiments (in the experimental and control groups) at least 7 days after the last experiment.

Each subject's weight and height were measured before the procedure. Anthropometric measures were used in cardiac impedance analysis, and as descriptive statistics of the studied population. All cardiovascular parameters were recorded by using a non-invasive method. We used disposable skin electrodes for impedance cardiography and a one-lead ECG.

The subjects were lying in the supine position and were asked to relax. All surface electrodes were connected to the computerized MP150 BIOPAC System for data recording. The duration of experimental protocol was about 30 minutes, and included three intervals: 10 minutes, pre-OMT rest phase (Rest); 8 to 12 minutes (about 10 minutes) of the OMT/Sham (Manipulations); and 10 minutes post-OMT recovery phase (Recovery).

OMT and sham manipulations were administered by an osteopathic physician. The participant lied supine with physician seated at the side of the table facing the participant. Cranial OMT included three techniques and was administered in the following sequence: occipital-atlantal decompression, occipital-mastoid joint, and compression of the fourth ventricle. Control subjects received the sham manipulative procedure or relaxed in supine position (non-touch control). The total duration of OMT was controlled by an osteopathic physician and was

about 10 minutes.

Occipital-atlantal decompression: Patient is in the supine position. The operator places the tip of a finger against the posterior tubercle of the atlas and holds that bone anteriorly, preventing it from moving posteriorly with the condyles as the patient nods or tips the head forward. This will release tension between the occipital condyles and the first cervical vertebrae.

Occipital-mastoid joint decompression: The occipital squama is gently moved forward and upward (anteriorly and superiorly) with the pads of the long finger, and the mastoid process of the temporal bone is lifted anterolaterally with the pads of the index fingers. This technique decompresses the jugular foramen, which the vagus nerve passes through.

Compression of the fourth ventricle: Manipulation is accomplished by having the operator's hands cupped to receive the lateral angles and supra-occiput on their thenar eminences. Gentle compression medially is maintained (generally 2 to 3 minutes) until tissue changes, such as a softening or increased motion, are noted in the supraoccipital area.

Sham: The osteopathic physician placed his hands on the skull of the subject but did not influence cranial motion. The sham manipulative procedure (SMP) was administered for 10 minutes.

All manipulations were administered by the osteopathic physician; experiments were conducted at Touro University Nevada. Data were collected by a non-invasive method using BIOPAC Systems, Inc. Equipment MP150 for data acquisition and analysis. The protocol consisted of three phases: rest before manipulations (10 min), manipulations (OMT) (approximately 10 min), and recovery after manipulations (10 min).

Data analysis: Most cardiovascular response variables were measured at baseline, immediately after manipulation ("immediate response"), and at the end of protocol ("after rest"). The immediate responses and at the end of protocol were calculated on a percentage basis relative to baseline to control some individual variations.

The percent response variables were each analyzed in a three-way analysis of variance (ANOVA) which included time ("Immediate response", "after rest"), treatment (cranial manipulation, sham), and sex (male, female) as fixed effects. For significant interactions in the ANOVA, a Bonferroni post-hoc test was used to compare treatment effects within time, sex, or both. The type I error rate (alpha) was set at 0.05. The relationships among dependent variables were described with Spearman correlations between percent response variables within. Analyses were done in Rv3.5.1 (R Core Team 2018).

Conditions

Conditions: Healthy Young Adults

Keywords: Osteopathic manipulations,
autonomic,
cardiovascular

Study Design

Study Type: Interventional

Primary Purpose: Basic Science

Study Phase: N/A

Interventional Study Model: Parallel Assignment

Number of Arms: 3

Masking: None (Open Label)

Allocation: Non-Randomized

Enrollment: 51 [Actual]

Arms and Interventions

Arms	Assigned Interventions

Experimental: Cranial OMT The experimental group received the three cranial osteopathic manipulative techniques, occipital-atlantal decompression (OAD), occipital-mastoid decompression (OMD), and compression of the fourth ventricle (CV4), consecutively applied.
	
Procedure/Surgery: Cranial manipulation group, or cranial osteopathic techniques (OMM) Cranial OMT procedure: Subjects were relaxed lying on the back for entire time of the research protocol (approximately 30 min). Osteopathic physician performed the osteopathic manipulations using his hands. The physician gently applied a small amount of force to the neck and head to release tissue tension until feeling a softening and warmth of tissues. Subjects experienced a sensation of slight pulling, releasing, or relaxing of the tissue.
 
Other Names:
 
• Cranial osteopathic manipulations, cranial osteopathic techniques, cranial OMT procedure

Sham Comparator: Sham manipulation The osteopathic physician placed his hands on the skull of the subject but did not influence cranial motion.
	
Procedure/Surgery: Sham manipulation The osteopathic physician placed his hands on the skull of the subject but did not influence cranial motion.
 
Other Names:
 
• Sham

No Intervention: Non touch group The control group whose members did not receive any manipulations.
	

Outcome Measures

Primary Outcome Measure:

1. Heart rate variability

The heart rate variability test was used to study the effect of OMT on heart rate and, by inference, on autonomic nervous system activity. A decrease in heart rate accompanied by an increase in vagal and decrease in sympathetic activity would indicate parasympathetic activation by OMT.

[Time Frame: The responses were measured immediately after the physician finished OMT/Sham (after Manipulations phase) and 10 minutes after post-OMT/Sham recovery phase (“Recovery”, “after rest”).]

2. Myocardial contractility

Changes in impedance cardiography parameters, such as stroke volume (SV) and cardiac output (CO), were used to evaluate the effect of OMT on myocardial contractility. An increase in cardiac output (CO) and stroke volume (SV) would indicate the stimulatory effect of selected OMT on myocardial contractility.

[Time Frame: The responses were measured immediately after the physician finished OMT/Sham (after Manipulations phase) and 10 minutes after post-OMT/Sham recovery phase (“Recovery”, “after rest”).]

3. Blood pressures

Systolic and diastolic blood pressure were measured by sphygmomanometer. A decrease in systolic blood pressure in response to OMT would indicate a decrease in vascular sympathetic tone.

[Time Frame: The blood pressure was measured manually before (before pre-OMT rest) and after the experimental procedure (after "Recovery" phase).]

Eligibility

Minimum Age: 21 Years

Maximum Age: 35 Years

Sex: All

Gender Based: No

Accepts Healthy Volunteers: Yes

Criteria: Inclusion Criteria:

Young adults

- Exclusion Criteria: Any pre-existing chronic cardiovascular diseases,
- Any pre-existing pulmonary diseases,
- Any pre-existing renal diseases,
- diabetes mellitus,
- endocrine disorders affecting the cardiovascular system,
- pregnancy,
- musculoskeletal conditions that can affect the use of the cranial OMTs, or
- acute illness that necessitates consulting a healthcare provider.

Contacts/Locations

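### Volunteers could re-enter in another arm of a study registered as parallel, and the stated ANOVA has no participant or session-order term, so any uneven spread of repeat sessions could bias the OMT contrast

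*Protocol*

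**What the plan says.** Three parts of the protocol bear on this point.

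- **Re-entry rule (Detailed Description).** "Participants were allowed to participate in multiple experiments (in the experimental and control groups) at least 7 days after the last experiment". The 7-day gap is the only condition attached. The document gives no rule for arm order and no limit on the number of returns.
- **Registered design (Study Design).** "Interventional Study Model: Parallel Assignment" and "Allocation: Non-Randomized", with no masking, three arms and an actual enrollment of 51. The 51 is not split by arm, and the document does not say whether it counts persons or sessions.
- **Stated analysis (Detailed Description, data analysis paragraphs).** Each response is "calculated on a percentage basis relative to baseline to control some individual variations". It then enters a three-way ANOVA with time (two points within a session), "treatment (cranial manipulation, sham), and sex (male, female) as fixed effects". For the error rate: "The type I error rate (alpha) was set at 0.05". No participant, session-number, period or previous-arm term is listed.

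The Brief Summary calls the work a controlled, non-randomized pilot with repeated measures.

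**The concern.** In a parallel study each person contributes to one arm. The re-entry rule expressly permits contribution to more than one, so the design label and the rule do not describe the same study.

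The consequence goes beyond labelling. A first-time volunteer meets the electrodes, the impedance leads and about 30 minutes of supine recording as something new; a returner does not. A returner who has had OMT also knows how it feels, and so is no longer naive when given sham in an unmasked study. Only people willing to come back supply later sessions. If arms differ in their share of such sessions, part of the difference in heart rate variability, stroke volume, cardiac output or blood pressure response is first visit against repeat visit rather than OMT against control. Allocation was not random, so chance cannot be relied on to even out those shares.

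**Working it through.** **1. The statements side by side.** Parallel assignment means one arm per person. The re-entry rule allows several arms per person. The phrase about repeated measures in the Brief Summary does not reconcile them, because the only repeated factor in the stated model is time within a session: the immediate response and the response after the recovery phase.

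**2. What the stated model can separate.** Its terms are time, treatment and sex. Time indexes the two readings within one session, not the first or second visit. No listed term therefore distinguishes a first session from a repeat. A participant term alone would handle correlation between sessions of the same person, but not an order effect aligned with arm; for that, session order must be in the model. The ANOVA names only cranial manipulation and sham, so the effect on comparisons with the non-touch group cannot be traced to a stated model.

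**3. What the existing safeguards do.**

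- The 7-day gap limits short-term carryover.
- The 10-minute supine rest and the percent-of-baseline scale reduce stable differences in level between people and between visits.
- Protection is weaker for blood pressure, because Outcome Measures places its first reading before the rest phase.
- None of these removes a change in the within-session response, lost naivety to sham, or selective return.

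**4. Size.** The protocol gives no SD, effect size or power figure, so there is nothing to reproduce. Suppose a repeat session shifts the percent response by d (in SD units), and the share of repeat sessions is p1 in OMT and p0 in control. With a simple additive shift:

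bias = d × (p1 − p0)

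Taking d as 0.2 to 0.5, an assumption with no anchor in the document:

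| Difference in repeat share | Bias (SD) |
|---|---|
| 0 | 0 |
| 0.25 | 0.05 to 0.125 |
| 0.50 | 0.10 to 0.25 |
| 1.00 | 0.20 to 0.50 |

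The sign depends on which arm holds more repeats and on the direction of the shift.

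**5. Illustrative false-positive rates.** These hold only if 51 counts independent sessions, split evenly over three arms (51/3 = 17 each) or over two (51/2, about 25 each), and the test is a two-sided normal test at 0.05. The protocol does not state sidedness.

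SE = √(2/n), which is √(2/17) = 0.343 SD or √(2/25) = 0.283 SD.

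Rate = Φ(b − 1.96) + Φ(−b − 1.96), with b = bias/SE.

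Example: bias 0.25 and n = 17 give b = 0.25/0.343 = 0.729 and a rate of 11.3%.

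| Share difference | n = 17 | n = 25 |
|---|---|---|
| 0 | 5.0% | 5.0% |
| 0.25 | 5.2 to 6.5% | 5.4 to 7.3% |
| 0.50 | 6.0 to 11.3% | 6.4 to 14.3% |
| 1.00 | 9.0 to 30.8% | 10.9 to 42.4% |

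The last row is an extreme corner. In it many people would probably be common to both arms, the contrast would be partly paired, and this SE would not apply.

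**The case against.** The strongest reply is that permission is not occurrence. Participants were allowed to return; the document does not say that any did, how many, into which arms or in what order. The number could be zero. A reader might infer that the trial was actually run as an unbalanced crossover and that its OMT contrast is biased. The text does not support that. The absence of an order rule is itself read from silence together with non-random allocation, not from a statement that order was left free. This objection stands, and it limits the point to a possible bias.

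A second reply is that the 7-day gap is not the only protection. That is right: the rest phase and the within-session baseline also help, though less for blood pressure.

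A third is that the percentages need inputs the document does not supply. If 51 counts persons and there were returners, there were more than 51 sessions. If 51 counts both persons and sessions, nobody returned. That also stands, and the rates are illustrations only.

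A fourth is that session-order terms usually belong in a statistical analysis plan, which is not at hand. This carries less weight here. The protocol itself sets the re-entry rule, the design label and the list of ANOVA terms, and these do not fit together as written.

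Finally, making first sessions the main analysis would be debatable. It discards within-person comparisons, which are useful in a non-randomized study, and could leave an arm with few sessions or none. It is better used as a sensitivity analysis.

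**Conclusion.** The point holds in a limited form. The parallel label and the re-entry rule conflict, nothing in the protocol reconciles them, and the stated ANOVA cannot tell session order from treatment. Bias follows only if people returned and repeat sessions were spread unequally across arms, if carryover differed by arm, or if return was selective. The protocol neither shows nor excludes this.

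The size cannot be computed from the document. Under an additive shift of 0.2 to 0.5 SD it runs from zero with equal repeat shares to 0.10 to 0.25 SD with a 50-point difference. A reader might take the highest illustrative error rates as the trial's actual false-positive rate. They are not: they need an extreme split, an assumed shift, and 51 independent sessions. Confidence is high in the conflict and in the missing terms, not in any realised bias.

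**What to change.** 1. Correct or qualify the parallel entry in Study Design so that it discloses re-entry across arms.
2. State whether 51 counts persons or sessions. Report persons and sessions per arm, the number of returners, and the order of arms each returner followed.
3. Wherever repeat sessions are analysed, add a participant term and session number to the ANOVA, and previous arm where the data allow. If returners nearly all followed one arm order, say so, because within-person data then cannot separate order from treatment.
4. Report a first-session-only comparison as a sensitivity analysis.

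The study is complete, so all of this uses sessions already recorded. The cost is a small re-analysis and an edit to the registry record. The sensitivity analysis loses some precision and, depending on the repeat count, could leave an arm thin. Balanced order, or adjustment for it, would deal with a simple additive shift. It would not by itself remove carryover that differs by arm or selective return, and none of these steps cures the non-random allocation.

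### Percent-of-baseline responses are analysed without a baseline covariate, which gives up precision and, in non-randomised arms, leaves the result resting on one unchecked assumption about baseline gaps

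*Protocol*

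**What the plan says.** The data analysis paragraph of the Detailed Description states that the immediate and end-of-protocol responses were "calculated on a percentage basis relative to baseline to control some individual variations". It continues: "The percent response variables were each analyzed in a three-way analysis of variance (ANOVA) which included time", and lists the remaining terms as "treatment (cranial manipulation, sham), and sex (male, female) as fixed effects". No baseline term is named, and no other handling of baseline is described. The significance level is fixed: "The type I error rate (alpha) was set at 0.05".

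The Brief Summary calls the trial a "This controlled not-randomized pilot study with repeated measures", and the Study Design section records "Allocation: Non-Randomized", with three arms and 51 enrolled.

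The same paragraph assigns the baseline, immediate and end-of-protocol measurements to most variables, not all. Under Outcome Measures, blood pressure is read only before the rest phase and after recovery.

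**The concern.** Dividing by baseline is the plan's only device for dealing with differences between people and sessions, and it does so only in part. A session that starts high for passing reasons tends to drift back and so gives a low percent response. A session that starts low tends to give a high one. This dependence on baseline stays in the error term of the ANOVA, and taking logs does not remove it.

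Two things are at stake. The first is precision: in a small study, error variance that a recorded covariate could explain is left in. The second is interpretation: nothing in a non-randomised design balances baselines between OMT and sham, so a baseline gap can carry over into the treatment contrast.

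**Working it through.** **Inputs from the protocol.** Percent response; model terms time, treatment and sex; alpha 0.05; 51 enrolled in three arms; non-randomised. The protocol gives no SD, correlation, effect size or power, so there is no stated figure to reproduce.

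**Assumed inputs.** 17 per arm (51/3; arm sizes are not given); equal baseline and follow-up SD s on the log scale, s = 0.5; r = 0.5, 0.7 and 0.9; effect 0.7 s; baseline gap d = 0.5 s; two-sided test. The simulations have sex in the model and one follow-up time. They ignore that one person may take part in several arms.

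**1. Precision.** The log ratio has variance 2(1−r)s² and slope −(1−r) on log baseline. With the covariate the residual variance is (1−r²)s². The ratio is (1−r²)/[2(1−r)] = (1+r)/2.

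| r | log ratio | with covariate | ratio |
|---|---|---|---|
| 0.5 | 1.00 s² | 0.75 s² | 0.75 |
| 0.7 | 0.60 s² | 0.51 s² | 0.85 |
| 0.9 | 0.20 s² | 0.19 s² | 0.95 |

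The inverse, 2/(1+r), means 33%, 18% and 5% more subjects for equal precision.

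**2. Power.** The standard error factor is √(2/17) = 0.343. The standardised effect is 0.7/(0.343·√(2(1−r))) = 2.04, 2.64 and 4.56 for the log ratio, and 0.7/(0.343·√(1−r²)) = 2.36, 2.86 and 4.68 with the covariate. The normal approximation gives 53, 75 and 99.5% against 65, 82 and 99.7%. Simulated t-tests run slightly lower:

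| r | raw percent | log ratio | log ratio + baseline |
|---|---|---|---|
| 0.5 | 45–46% | 50–51% | 60–62% |
| 0.7 | 69–70% | 72–73% | 77–78% |

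The covariate's own share is the step from the second column to the third, about 11 and 5 to 6 points. The step from the first to the second belongs to the log. At r = 0.9 power is already at its ceiling for this effect, so nothing is gained.

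**3. False positives with no OMT effect.** Three mechanisms were compared, at r = 0.5 / 0.7 / 0.9.

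- *Gap of 0.5 SD that regresses to a common mean.* The log ratio is biased by −(1−r)d = −0.25, −0.15 and −0.05 SD. The test statistic shifts by 0.5·√((1−r)/2)/0.343 = 0.73, 0.56 and 0.33, so rejection is about 11, 9 and 6% by the normal approximation. Simulated raw percent: 9–10, 7–8 and 6–7%, with spurious differences of about −13, −8 and −3 points. The covariate model stays at about 4–6%.
- *Gap of 0.5 SD that is stable and persists.* The percent response is unbiased (about 5%). The covariate model is off by +(1−r)d, a shift of 0.5·√((1−r)/(1+r))/0.343 = 0.84, 0.61 and 0.33, so about 13, 9 and 6% (simulated 12–13, 8–9 and 6%).
- *Chance imbalance only* (SD 0.34 baseline SD). Both analyses stay at about 5%.

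The point differences depend on spread. In a second simulation at r = 0.5, the spurious difference was about 3 points at a CV of 12%, 6–7 at 25% and 21–25 at 80%.

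**The case against.** Choosing between change from baseline and baseline adjustment in non-randomised groups is a choice between two assumptions that the data cannot settle. Volunteers who end up in different arms may well differ in stable traits. In that case the percent response is the unbiased analysis and the covariate creates the error. This stands: the figures under the second mechanism are as large as those under the first, and the protocol does not say which applies.

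A reader might therefore infer too much in three ways.

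- That the plan produces spurious OMT effects, or that the covariate removes confounding. The documents support neither. The bias appears only if the gap is transient, and it changes sides if the gap is stable.
- That a typical chance gap of 0.34 SD inflates type I error. Averaged over chance imbalance, it does not.
- That every OMT-versus-sham test, blood pressure included, uses this response in this model. Only most variables have the two post-baseline times. Blood pressure has a single later reading, so the time factor cannot apply to it as written.

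It can also be said that the protocol claims only to control some of the variation, which is true, and that covariates may be left to an SAP. The first is fair. The second has less force, because the protocol writes the model out term by term and gives its reason for the percentage step. What remains is a valid precision point, modest at high r, and a case for showing both analyses.

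**Conclusion.** The point holds in a limited form. The written model leaves recoverable precision unused: residual variance could fall by 25, 15 or 5% at r = 0.5, 0.7 or 0.9 relative to the log ratio. This rests on similar variances at baseline and follow-up and on no systematic baseline difference between arms. The power gains also rest on the assumed arm size and effect.

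On bias, the conclusion is symmetric. At a 0.5 SD gap the percent response alone can reach about 6 to 10% false positives under one mechanism, and the covariate model alone about 6 to 13% under the other. Neither is safe by itself in non-randomised arms, and the plan reports only one. Near r = 0.9 all of these effects are small.

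**What to change.** For each outcome measured at both post-baseline times (HRV indices, heart rate, stroke volume, cardiac output), add the session's own baseline value as a covariate, logged for skewed HRV indices. Use the log ratio or the log follow-up value as response. With log baseline in the model the two give the same treatment estimate.

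Report this next to the unadjusted percent or log-ratio analysis. Agreement supports an OMT effect as far as baseline imbalance is concerned. Disagreement signals that baseline imbalance may explain the result. For blood pressure, fit a model without the time factor and with the pre-session systolic or diastolic reading as covariate.

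The cost is one degree of freedom per model and a re-analysis of data already collected, since every percent response needed its baseline. The drawback is over-correction if the arms differ in stable trait levels, which is why the unadjusted analysis stays beside it.

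### The three-way ANOVA names no subject or session error term, although sessions give two responses from one baseline and volunteers may return, so the 5% level is not assured

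*Protocol*

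**What the plan says.** The model is set out in the Data analysis paragraph of the Detailed Description: "The percent response variables were each analyzed in a three-way analysis of variance (ANOVA) which included time" (two levels, immediate response and after rest), "treatment (cranial manipulation, sham), and sex (male, female) as fixed effects". The type I error rate is 0.05. Follow-up comparisons depend on the interaction tests: "For significant interactions in the ANOVA, a Bonferroni post-hoc test was used to compare treatment effects within time, sex, or both".

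The same paragraph defines the responses: "The immediate responses and at the end of protocol were calculated on a percentage basis relative to baseline". Under Outcome Measures, both heart rate variability and myocardial contractility have two post-baseline time points: "The responses were measured immediately after the physician finished OMT/Sham (after Manipulations phase) and 10 minutes after post-OMT/Sham recovery phase". Blood pressure differs: "The blood pressure was measured manually before (before pre-OMT rest) and after the experimental procedure", so it gives one response per session.

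The Detailed Description lets people come back: "Participants were allowed to participate in multiple experiments (in the experimental and control groups) at least 7 days after the last experiment". The Brief Summary describes the design as "This controlled not-randomized pilot study with repeated measures". No subject term, session term, random effect or error stratum is named anywhere.

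**The concern.** A fixed-effects ANOVA with one pooled residual holds its level only if the rows are independent. Two features stated in the protocol break that.

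- **Two rows per session.** The immediate and after-rest responses come from the same person on the same day and share one baseline. Noise in that baseline enters both, so positive correlation is expected.
- **Returning volunteers.** One person may supply sessions under both treatment levels.

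The first makes the between-session tests (treatment, sex, treatment-by-sex) too liberal and the within-session tests (time, time-by-treatment) too conservative. The second can push the treatment test to either side of 5%. The treatment test is the study's main question for two of its three primary outcomes. The interaction tests are the gate to the Bonferroni comparisons, so that gate opens too readily for sex and too rarely for time.

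**Working it through.** **Inputs from the protocol.** Alpha 0.05; time, treatment and sex with two levels each; two responses per session for heart rate variability and impedance variables; 51 enrolled in three arms.

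**Assumptions, not in the protocol.** Within-session correlation ρ from 0.2 to 0.9; 51/3 = 17 sessions per arm; sexes equally split; number of returners varied. With 25 sessions per arm the results agree within 0.7 points.

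**Step 1: reproduce the stated level.** With independent rows (ρ = 0), the simulated ANOVA rejects in 4.5% to 5.1% of null trials across the main effects and two-way interactions (8 sessions per treatment-by-sex cell). The 5% level is therefore reproduced, but only under independence.

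**Step 2: two responses per session, nobody returns.** Let each response have variance σ². The pooled residual still estimates σ².

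- The mean of a session's two responses has variance σ²(1+ρ)/2, but the model uses σ²/2. The treatment F is inflated by (1+ρ), and its actual level is 2(1 − Φ(1.96/√(1+ρ))).
- The difference between the two responses has variance 2σ²(1−ρ), but the model uses 2σ². The time-by-treatment level is 2(1 − Φ(1.96/√(1−ρ))).

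At ρ = 0.5, 1.96/√1.5 = 1.600 gives 11.0%, and 1.96/√0.5 = 2.772 gives 0.56%. The power column below is simulated, for a time-by-treatment effect that has 80% power under the session-level error.

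| ρ | Treatment, formula | Treatment, simulated | Time-by-treatment, formula | Time-by-treatment, simulated | Power instead of 80% |
|---|---|---|---|---|---|
| 0.2 | 7.4% | 7.4% | 2.8% | 2.9% | 74% |
| 0.3 | 8.6% | 8.3% | 1.9% | 2.1% | 69% |
| 0.5 | 11.0% | 10.7% | 0.56% | 0.7% | 53% |
| 0.67 | 12.9% | 12.9% | 0.06% | 0.1% | 30% |
| 0.8 | 14.4% | 14.5% | about 0% | about 0% | 8% |
| 0.9 | 15.5% | 15.8% | about 0% | about 0% | not run |

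Treatment-by-sex agrees with treatment within 0.3 points. Treatment contrasts within a single time point keep 4.9% to 5.3%. Treatment contrasts within sex, averaged over time, run at 7.3% to 14.5% for ρ 0.2 to 0.8; these are rates per contrast, before the gate and Bonferroni.

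**Step 3: how large might ρ be?** If the baseline error variance is k times the post-baseline error variance and all errors are independent, the shared baseline alone gives ρ of about k/(1+k): 0.20, 0.33 and 0.50 for k = 0.25, 0.5 and 1. On the percent scale, with coefficients of variation of 5% to 30%, simulation gives 0.20–0.22, 0.34–0.40 and 0.51–0.61. A ρ of 0.5 is plausible but not forced.

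**Step 4: volunteers cross arms.** If everyone gives one session in each arm and sessions of the same person correlate at τ, the factor becomes (1+ρ−2τ) for treatment and (1+ρ+2τ) for sex. For ρ = 0.5 and τ = 0.4 these are 0.7 and 2.3, giving 1.9% and 19.6% (simulated 2.3% and 19.6%). Over 25%, 50% and 100% overlap, ρ of 0.3, 0.5 and 0.8, and τ from 25% to 75% of ρ, the treatment test ranges from 1.6% to 13.2%. Time-by-treatment stays at about 2% (ρ 0.3), 0.6–0.8% (0.5) and about 0% (0.8).

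**Step 5: does the remedy restore 5%?** With no returners, session-level tests run at 4.8% to 5.2%. With returners, a random person intercept on session means (Satterthwaite degrees of freedom) gives 4.3–5.1% when all cross, but 6.1–7.4% when 25–50% cross, because the person variance is then poorly estimated.

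**The case against.** The strongest reply is that the text is silent rather than wrong. It lists fixed effects and does not say that no random term was used, and the Brief Summary speaks of repeated measures. A subject term may have been fitted, and an analysis plan not at hand might record it. That possibility stands, and the fix allows for it. But the protocol itself lists the model's terms and sets the 5% level; the design label does not supply the missing term.

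Second, the size depends on figures the protocol does not give, and returners could cancel the inflation of the treatment test. This also stands. It is why the conclusion is that the level is not assured, not that it is always inflated.

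Third, the within-sex rates of 7.3–14.5% ignore the gate. This is correct. With the treatment-by-sex gate and Bonferroni over two sexes, a false within-sex finding occurs in roughly 4% of trials at ρ 0.2 and 9% at ρ 0.8, against about 2% under independence. Inflation remains, but the absolute rate is below 5% at the low end.

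Fourth, a person intercept does not guarantee 5% when only some volunteers return. That is true and calls for a sensitivity analysis.

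Finally, this is a non-randomised, open-label pilot, so a corrected error term would not make its p-values confirmatory. The study nevertheless declares a 5% level and uses significance as a gate.

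**Conclusion.** The concern holds. As listed, the model has the wrong error terms for heart rate variability and impedance variables. With one session per person and ρ between 0.2 and 0.8, the treatment test runs at about 7% to 15% and time-by-treatment at about 3% down to nearly zero. With returners, the treatment test can lie on either side of 5%. These sizes rest on assumed values for ρ, sessions per arm and overlap. Blood pressure is affected only through returning volunteers. Confidence is medium, because a subject term may have been used and not reported. The point should be fixed, but the data need not be collected again.

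**What to change.** - If a subject term was fitted, state it and its form in the Data analysis paragraph.
- If not, re-analyse heart rate variability and impedance variables with a linear mixed model: fixed time, treatment, sex and their interactions; a random intercept for person and, where volunteers returned, for session within person; Kenward-Roger or Satterthwaite degrees of freedom. Take the Bonferroni contrasts from that model.
- For blood pressure, drop time and keep the person term.
- Report how many volunteers gave more than one session and in which groups.
- Add a sensitivity analysis using each person's first session only, since the person variance is weakly estimated if few returned.

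The cost is a change of wording and a re-analysis of data in hand. Some treatment p-values may become less favourable.
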